The study will consist of 3 study visits in total. The first visit will involve the diagnostic assessment and medical screen to determine eligibility for the study, in addition to the administration of clinician-administered and self-report questionnaires. This visit will take approximately 2.5 hours to complete. If participants are eligible, they will be asked to return to the clinic for two additional study visits, which will be identical in procedure and take approximately 2 hours each to complete. Female participants must complete Visits 2 and 3 during the active phase of their contraceptive medication (e.g. not during their menses); female subjects using multiphasic contraceptives must be on the same dose of ethinyl estradiol for both Visit 2 and 3. Participants will be instructed to avoid alcohol, caffeine, and nicotine for 24 hours prior to Visits 2 and 3. These visits will involve the administration of both an oxytocin and placebo nasal spray, in randomized order, and the completion of various social cognition tasks. They will be separated by a one-week washout period (**maximum 28 day** window period). The study design and procedures are represented in the following schematic:

[figure not shown]
Diagnostic Assessment and Medical Screen:

After obtaining informed consent, participants will be administered the Structured Clinical Interview for DSM-IV (SCID-I/P; First, Spitzer, Gibbon, & Williams, 2002) to determine diagnostic eligibility. The SCID allows the investigator to assess all diagnostic inclusion and exclusion criteria. Participants who are recruited for the healthy control

group will be given the SCID-I/P to confirm the absence of Axis I psychopathology. Participants who meet the diagnostic inclusion and exclusion criteria will be given a medical screen consisting of a history and physical examination (H&P) by a study nurse or physician to determine the participant's eligibility and safety for the study. In addition, a urine pregnancy test will be given to females during this visit, as well as at the beginning of Visits 2 and 3 to ensure continued eligibility.

Investigational Agent (dose, method, schedule of administration, dose modifications):

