Mini-Markers Scale (MM; Saucier, 1994): The Mini-Markers Scale is a 40-item self-report measure of the five factor model personality factors: extraversion, agreeableness, conscientiousness, emotional stability, and openness. It asks participants to rate how accurately each item describes themselves on a 1-9 point Likert scale ranging from "extremely inaccurate" to "extremely accurate."

Adverse Events Form: This self-report form will be administered at Visits 2 and 3 after nasal spray administration to assess for any adverse events. Participants will be asked to report on a symptom checklist whether they experienced a negative reaction to the oxytocin and placebo nasal sprays. If participants endorse 'yes' on any item, a study clinician or nurse will follow up and ask them whether the symptom resolves by the end of the study visit.

Assessment of Blind Form: This questionnaire will be given at Visits 2 and 3 after nasal spray administration to assess for participants' expectancies regarding the drug they received. Participants will be asked which nasal spray they believe they received (oxytocin or placebo), to rate their degree of certainty, and to describe their reasons why.

Tasks:

The following tasks will be administered at each study visit approximately 45 minutes after drug administration. The order of tasks will be the same within each participant in the study between Visit 2 and Visit 3 in order to minimize variance for the within-subject analysis and isolate the effect of the drug. However, the order of tasks will be counterbalanced between participants in the study, to account for possible carry-over effects.

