Potential risks associated with intranasal oxytocin include headaches, nausea, and allergic dermatitis ($\geq 1/10,000$, $<1/1,000$), and uterine contractions ($< 1/10,000$), per Novartis Basic Prescribing Information for Syntocinon®. Additional sources of discomfort may include lightheadedness, nasal irritation, or dry mouth/throat, although these appear to be mild (MacDonald et al., 2011). Participants with any serious adverse events will be immediately withdrawn from the study. The half-life of oxytocin is approximately three minutes when administered intravenously, therefore, it will not remain in the system for very long.

Regarding the use of TestMyBrain.org, the following steps will minimize risk to subjects:

- (1) **Identifying Information:** TestMyBrain does not collect any uniquely identifying information about the participant, including birth date or IP addresses. A participant will only be linked to his/her data through the participant codes generated by the external researcher and the participant will not be identifiable based solely on information in TestMyBrain databases.

- (2) Data Transfer between Client (Browser) and Server: TestMyBrain uses SSL (secure sockets layers) encryption to protect any information that is being transferred between a browser and server and all study-specific links will use secure communications protocols incorporating SSL (https).
- (3) Database and Web Hosting: All data is stored through TestMyBrain.org in custom MySQL databases provided by the host and managed by TestMyBrain investigators. TestMyBrain is currently hosted through Rackspace, which offers added customer support and security benefits <http://www.rackspace.com/>. Their comprehensive privacy policy insures that they will not have access to any of the data that goes through TestMyBrain without permission or unless required by law: <http://www.rackspace.com/information/legal/privacystatement>. Rackspace offers an automatic backup system with nightly updates.
- (4) Monitoring and Quality Assurance: TestMyBrain.org has been in operation since 2008, with numerous collaborations resulting in a dozen peer-reviewed papers and over 900,000 participants. No complaints or incidents have been reported that would indicate a privacy, security, or personal risk to participants.

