Data gathered from this study may benefit other individuals with BDD in the future. To date, no studies have examined the oxytocin system in BDD. Given the mounting evidence for oxytocin's role in social and cognitive deficits in autism spectrum disorders, schizophrenia, and other disorders, it is clear that the effects of oxytocin have transdiagnostic implications. Our findings may show that a single administration of intranasal oxytocin may alter social cognitive processes thought to maintain BDD. More importantly, if study aims are achieved, we may learn how to improve treatments for BDD, and identify individuals who would be responsive to oxytocin. Thus, the current study represents a translational approach to investigating potential pathophysiological mechanisms underlying BDD, and will advance knowledge regarding the potential of a promising novel therapeutic agent for BDD.

IX. Monitoring and Quality Assurance

Data and Safety Monitoring Plan:

The study will be monitored for quality assurance and adherence to the protocol according to the following monitoring plan:

A Data Safety and Monitoring Board (DSMB) will be formed consisting of three members who are not associated with the study. The purpose of the DSMB is to: (1) review all adverse events, (2) assess the timeliness, completeness, and quality of the data collected, (3) assess the adherence to protocol requirements, especially measures taken to protect participant safety, and (4) assess the benefit/risk ratio of study procedures. The DSMB will meet once after 40 subjects have been enrolled, and will be provided with the following data prior to this meeting: (1) all adverse events reported, and (2) subject recruitment, enrollment, and dropout numbers. During the meeting, the board will review these data and have 30 days to generate a report, which reflects their opinion of whether the study should be permitted to continue and whether any changes need to be made. This report will then be submitted to the IRB. If any serious adverse events occur during the study, DSMB members will be apprised of them within 24 hours of the event and will be provided unblinded information with regard to the participants' treatment assignment and corresponding study visit. DSMB members will then provide suggestions for the progress of the study, as well as determine whether modifications to the protocol are needed.

Adverse Event Reporting Guidelines:

Definitions:

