1. **Adverse event** means any untoward or unfavorable medical occurrence in a human subject, including any abnormal sign (for example, abnormal physical exam or laboratory finding), symptom, or disease, temporally associated with the subject's participation in the research, whether or not considered related to the subject's participation in the research (modified from the definition of adverse events in the 1996 International Conference on Harmonization E-6 Guidelines for Good Clinical Practice).
2. **Serious adverse event** means any event temporally associated with the subject's participation in research that meets any of the following criteria:
 - results in death;
 - is life threatening (places the subject at immediate risk of death from the event as it occurred);
 - requires inpatient hospitalization or prolongation of existing hospitalization;
 - results in a persistent or significant disability/incapacity;
 - results in a congenital anomaly/birth defect; or
 - any other adverse event that, based upon appropriate medical judgment, may jeopardize the subject's health and may require medical or surgical intervention to prevent one of the outcomes listed above (examples of such events include allergic bronchospasm requiring intensive treatment in the emergency room or at home, blood dyscrasias or convulsions that do not result in inpatient hospitalization, or the development of drug dependency or drug abuse).
3. **Unanticipated problem involving risks to subjects or others** means any incident, experience, information, outcome, or other problem that is *unexpected* and related to the research, and that indicates that the research places subjects or others at an increased risk of physical, psychological, economic, legal, or social harm than was previously known or recognized.
4. **Unexpected** means that the incident, experience, or outcome is unexpected (in terms of nature, severity or frequency) given the (a) research procedures that are described in the protocol- related documents, such as the IRB-approved research protocol and informed consent document and (b) the characteristics of the study population being studied.

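### No active adverse event query is described between Visits 2 and 3, before the second spray, or after Visit 3, and unresolved symptoms have no stated follow-up beyond the visit

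*Combined protocol and SAP*

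**What the plan says.** Section V (Self-Report Questionnaires, Adverse Events Form) describes the collection: "This self-report form will be administered at Visits 2 and 3 after nasal spray administration to assess for any adverse events". On its content: "Participants will be asked to report on a symptom checklist whether they experienced a negative reaction to the oxytocin and placebo nasal sprays". If any item is endorsed, "a study clinician or nurse will follow up and ask them whether the symptom resolves by the end of the study visit". The paragraph mentions no recall period, onset date, pre-spray baseline or later follow-up.

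Section V (Overview of Study Procedure) fixes the schedule: "The study will consist of 3 study visits in total". The first is screening. The two dosing visits last about 2 hours each and are separated by a one-week washout with a 28-day maximum. The only recheck described for the start of Visits 2 and 3 is the urine pregnancy test for females (Diagnostic Assessment and Medical Screen).

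Section IX (Definitions) defines an adverse event as "any untoward or unfavorable medical occurrence in a human subject" that is linked in time to taking part, regardless of judged relatedness. Section VII states that a participant with any serious adverse event is withdrawn at once. Section IX (Data and Safety Monitoring Plan) states for serious events that "DSMB members will be apprised of them within 24 hours of the event", with unblinded assignment and the visit concerned. The DSMB meets once, after 40 participants are enrolled, and receives the adverse events reported.

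**The concern.** The definition and the collection do not cover the same ground. The definition covers any untoward event during participation. The form, as described, asks about reactions to the sprays, within two visits of about 2 hours. Three things follow.

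- **Completeness.** Anything that starts after a participant leaves, or is still present on leaving, enters the record only if the participant raises it. The record that reaches the DSMB and the IRB is no more complete than the form plus spontaneous reports.
- **Attribution.** In a crossover, the tolerability comparison depends on placing each event in the right period. The Visit 3 form comes after the second spray, so an event that began between visits may first be written down after the other product has been given.
- **Acting on the protocol's own rule.** For an event between visits, the last point at which the withdrawal rule can take effect before further exposure is just before the second spray. No adverse event question is described there.

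**Working it through.** The plan states no figure on this point, so there is nothing to reproduce. The check sets the passages side by side and adds simple arithmetic.

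**Inputs.** Dosing visit about 2 h; interval 7 days, maximum 28 days; 3 visits in all (section V, Overview). 40 participants planned, at most 50 enrolled (section III). Syntocinon frequency for allergic dermatitis below 1 in 1,000 (section VII).

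**Step 1: where an adverse event question is described.**

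| Time | Active query described? |
|---|---|
| Visit 2, after spray | Yes, checklist |
| Leaving Visit 2 to start of Visit 3 | No |
| Visit 3, before spray | No (pregnancy test only) |
| Visit 3, after spray | Yes, checklist |
| After Visit 3 | No; no further visit |

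**Step 2: share of time under scheduled observation after the first spray.** Share = visit length / time to the next visit.

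- 7 days: 2 / (7 × 24) = 2 / 168 = 1.2%, leaving 168 − 2 = 166 h without a query.
- 28 days: 2 / (28 × 24) = 2 / 672 = 0.3%, leaving 672 − 2 = 670 h.
- After the second spray: observation ends with the visit, and no later contact is scheduled.

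The 2 h is an upper limit, because the spray is given some time into the visit.

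**Step 3: each rule against the information it needs.**

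- *Definition of an adverse event:* needs events outside the visit, related or not. The form covers reactions to the sprays within the visit.
- *Withdrawal after a serious event:* needs interval events known before the second spray. No query is described at that point.
- *DSMB notice:* the 24 hours run from the event. For an event outside the clinic, staff can act only once they know of it, so the deadline as worded cannot be guaranteed.
- *Period of an event:* needs an onset date, or a query before the second spray. Neither is described.

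**Step 4: how often this might matter.** The documents give no rate of delayed or persistent reactions. Purely as an illustration, let q be the assumed probability of one per spray among 40 independent participants. Expected number = 40q; chance of at least one = 1 − (1 − q)^40.

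| Assumed q | Expected per spray | Chance of at least one |
|---|---|---|
| 1% | 0.4 | 33% |
| 2% | 0.8 | 55% |
| 5% | 2.0 | 87% |

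For one named reaction a ceiling can be set: allergic dermatitis at below 1 in 1,000 gives fewer than 40 × 0.001 = 0.04 expected cases in 40 participants, each receiving one oxytocin dose.

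**The case against.** The strongest case is that the protocol does not confine safety information to the visit. Section IX (Reporting Requirements) requires unanticipated problems to be reported even after a participant has finished. Section V gives the study physician oversight of reported events. For serious events the DSMB receives the assignment and the visit. Consent and contact pages are not in the available text and may tell participants whom to call. The form itself is not reproduced either, so it may hold onset fields. There is one oxytocin dose per participant, safety is not among the aims, and section VI plans no adverse event analysis.

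Much of this stands, and it rules out several stronger readings:

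- **That later events are lost, or that staff have no route to learn of them.** The reporting rules presuppose spontaneous reports. What the text supports is that no active query is described, so events may be missed unless volunteered.
- **That events are credited to the wrong spray.** This is a risk arising from the order of the form and the second spray, not something the plan states. Naming both sprays in the form's description can be read as covering the two visits collectively.
- **That unresolved symptoms have no outcome.** Their status at the end of the visit is asked. A later outcome is what is missing.
- **That the protocol sets the observation period by half-life and contradicts itself.** Section VII says "The half-life of oxytocin is approximately three minutes when administered intravenously, therefore, it will not remain in the system for very long", but as a general remark on risk. No section uses it to set the length of observation. Section V says "The following tasks will be administered at each study visit approximately 45 minutes after drug administration", and that time falls inside the 2-hour visit, so the two statements do not conflict on adverse event capture.

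What the objection does not answer is that reporting rules act on events already known. They schedule no collection, and telephone instructions in a consent form would still be passive.

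**Conclusion.** The point holds as a gap in active ascertainment. The described procedure asks about adverse events only after the spray at two visits and follows symptoms only to the end of the visit. It leaves 166 to 670 hours before the second spray, and all time after Visit 3, without a described query. That is narrower than the protocol's own definition, and it gives the withdrawal rule no described check before the second exposure.

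The number of events affected cannot be estimated from the documents. The hours measure unqueried time, not missed risk, and the 33% to 87% range rests wholly on assumed rates. The conclusion assumes that neither the adverse event form nor the removed pages contain a scheduled query. If the form already has onset dates and asks about the interval, the attribution part shrinks, but the query would still come after the second spray.

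This does not touch the primary efficacy analysis. It is worth changing because the remedy is nearly free and improves both safety information and attribution between sprays. A reader might infer that the trial would report good tolerability only because it stopped asking; the documents do not support that.

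**What to change.** 1. **Main change, Adverse Events Form paragraph (section V).** At Visit 3, before the spray, ask about any event since Visit 2. Record onset and resolution dates, enter the event in the Visit 2 period, and keep this record separate from the post-spray form. At the same query, update the outcome of any symptom unresolved at the end of Visit 2.
2. **Optional.** Add one brief contact by blinded staff after Visit 3, using the same checklist, to record late events and the outcome of symptoms unresolved at that visit.
3. **Data and Safety Monitoring Plan (section IX).** Reword the 24-hour DSMB notice to run from staff awareness of the event.

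The withdrawal rule in section VII should be reconciled with the visit procedures so that the information it depends on is sought before the second spray. Its clinical content is not at issue here.

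Cost: protocol wording, a few minutes at Visit 3, and, if the option is taken, up to about 40 to 50 short contacts. Some unrelated interval events will also be recorded, which the protocol's definition already calls for.

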Posner Task (Posner, 1980; Posner, Snyder, & Davidson, 1980): The Posner Task is a spatial cueing paradigm that measures attentional engagement toward and disengagement from certain visual cues. The stimuli for this task will be modified to include a set of disgust, happy, and neutral faces. The task will consist of 360 trials. During each trial, the participant will see a fixation cross. On each trial, a face (disgust, happy, or neutral) will appear within either the top or bottom half of the screen (the other half of the screen will remain blank) and then disappear. Then, a probe (the letter "E" or "F") will appear in the top or bottom half of the screen. The participant will be instructed to identify the letter as quickly and accurately as possible by clicking the left or right mouse button (left for "E", right for "F"). Upon responding, the next trial will commence.

For valid trials, the probe will appear in the position previously occupied by the face stimulus, whereas for invalid trials, the probe will appear in the empty half of the screen. Response latencies for valid and invalid trials will reflect the participant's attentional engagement towards threat and disengagement from threat, respectively, and will be used to calculate attentional bias scores for threat cues.

Trust Game: The participant will be told that he will be playing the Trust Game with another player in a different room, and that both players will be allocated a sum of 10 game dollars to start the game. The participant will be told that he will take the role of Player 1. The instructions for the game will be as follows: Player 1 will have the opportunity to transfer all, some, or none of his 10 game dollars to Player 2, the sum given by Player 1 will be tripled, and Player 2 will have to choose to return some, all, or none of his game dollars to Player 1. The role of Player 2 will be played by a member of the study staff. The participant will play the Trust Game twice. The amount of money given by the participant is recorded and represents a measure of "trust". Three game dollars will equal \$1. The subject will be paid the value of this amount in dollars.

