- (5) Protection from Malicious Attack: The TestMyBrain system is implemented as a virtual Linux host, so the primary danger from malware is malicious SQL injection attacks. To guard against this, all entered data are sanitized before being included in any SQL updates.
- (6) Transmission of Data: Participant test data and codes will be transmitted directly from the TestMyBrain.org database to the external researcher using either secure http file transfer or secure SQL connection protocol.
- (7) Storage of Data: Once the study is complete and all data have been downloaded from TestMyBrain.org databases, participant codes that are retained in TestMyBrain databases will be destroyed along with any other study-specific information or information linking a particular testing session with the external research study.

Other Risks:

Information obtained from participants will be treated confidentially. There may be some discomfort associated with nasal spray administration. Nurses at the MGH Clinical Research Center are highly skilled in educating patients about nasal spray use and sensitive to expressions of discomfort. There may also be mild discomfort associated with responding to questions during the diagnostic assessment and answering multiple questionnaires about negative symptoms. Participants will be told that they can refuse to answer any questions that they do not want to answer, and that they can withdraw participation at any point without penalty. Participants with an emergent need for immediate psychiatric care will be referred to the Acute Psychiatry Service at MGH.

VIII. Potential Benefits

Potential Benefits to Participating Individuals:

There are no immediate benefits to the individual for participating in this study. Participants with BDD may receive feedback regarding their symptoms. In the case that participants need referrals for psychiatric treatment, we will facilitate those referrals to MGH or other appropriate facilities. Participants will be provided compensation for their time, in a pro-rated hourly amount of \$15/hour, with a maximum of \$100, plus any additional earnings from the Trust Game (up to \$20), by the end of the study visit for completing all study procedures. In addition, participants will be compensated for parking and public transportation costs such that participants are not responsible for any costs associated with participating in the study.

Potential Benefits to Society:

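### The Trust Game is repeated at Visits 2 and 3 against a staff-played partner, with no fixed return rule and nothing withholding results until the last game, so experience that differs by drug or diagnosis can enter a primary outcome

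*Combined protocol and SAP*

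**What the plan says.** All references are to the combined protocol and SAP.

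- **Repetition.** Under V. Study Procedures, Tasks: "The following tasks will be administered at each study visit approximately 45 minutes after drug administration". The Trust Game is one of these tasks, and the Overview of Study Procedure has Visits 2 and 3 follow the same procedure.
- **Partner and number of plays.** The Trust Game paragraph states: "The role of Player 2 will be played by a member of the study staff. The participant will play the Trust Game twice". It does not say whether twice means once per visit or twice at each. In the game instructions, "Player 2 will have to choose to return some, all, or none of his game dollars to Player 1". No script or return rule is given, and no time is stated at which the participant sees the return.
- **Blinding.** Under Treatment Assignment Procedures, everyone except the research pharmacy is blind to drug condition. Blinding of Player 2 to diagnosis is not mentioned.
- **Payment.** Three game dollars are worth $1, and "The subject will be paid the value of this amount in dollars". VIII. Potential Benefits caps game earnings at $20, paid "by the end of the study visit for completing all study procedures".
- **Protection between visits.** "They will be separated by a one-week washout period", with a 28-day maximum. Spray order is randomised. Task order is counterbalanced between participants but held the same within a participant.
- **Analysis.** Under Aim 1 Analyses, Hypothesis 1a regresses the placebo score on diagnosis. Hypothesis 1b regresses the oxytocin score on diagnosis, adjusting for the placebo score. Neither model has a visit or sequence term. The outcome named there is the back-transfer amount, whereas the task description records the amount the participant gives.

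**The concern.** A trust game played more than once tells the player something about the partner. If the participant sees the return at Visit 2, the transfer at Visit 3 may reflect that experience as well as the spray. A washout clears a drug; it does not clear a belief about whether the other player pays back.

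Randomised order balances a shift that is the same for everyone. It does not balance a shift that depends on what happened at the first visit. If oxytocin raises the first transfer, the return can differ from the one that follows a first visit on placebo, so the carry-over can differ by sequence.

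There are three routes to a difference by diagnosis. Hypothesis 1b itself expects a larger oxytocin effect in BDD, so first-visit transfers, and hence returns, may differ more in that group. Rejection sensitivity is a planned moderator, so the groups may react differently to a poor return. And nothing prevents a staff member who knows the diagnosis from setting returns differently. At stake is one of the two primary outcomes.

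**Working it through.** **1. Are returns part of what the participant is paid?** Inputs: 10 game dollars sent at most, tripled; 3 game dollars = $1; $20 cap.

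- Two plays, full tripled sum returned: 2 × 30/3 = $20, which equals the cap.
- Two plays, only the amount sent is paid: 2 × 10/3 = $6.67.
- Two plays, Player 2's own 10 also returned: 2 × 40/3 = $26.67.

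The cap fits two plays with the tripled sum returned, so returns appear to be part of the payment.

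**2. Does the payment text show that results are known before Visit 3?** The visits last about 2.5 + 2 + 2 = 6.5 hours. At $15 per hour that is 6.5 × 15 = $97.50, just under the $100 maximum in the same sentence. The sentence therefore seems to describe the whole study, and payment may fall at the last visit. It does not establish disclosure before Visit 3, and nothing else in the documents rules disclosure out.

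**3. Size of the bias.** For one diagnosis group let τ be the oxytocin effect, s the ordinary Visit 3 minus Visit 2 shift, and c_P and c_O the extra shift carried from a first visit on placebo or oxytocin. The oxytocin minus placebo difference is:

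- placebo first: τ + s + c_P
- oxytocin first: τ − (s + c_O)
- average with balanced sequences: τ + (c_P − c_O)/2

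The Power and Sample Size section compares this difference between BDD and controls. Writing Δ for BDD minus control:

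- bias in that contrast = ½ Δ(c_P − c_O)
- s cancels, and so does any c_P − c_O that is the same in both groups.

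For Hypothesis 1a, placebo scores from the oxytocin-first half are taken at Visit 3:

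- mean placebo score = μ + ½(s + c_O)
- bias = ½ Δ(s + c_O)

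The documents give no value for these shifts. Taking the group difference as an assumption:

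| Assumed group difference (game dollars) | Bias, either direction |
|---|---|
| 0 | 0 |
| 0.5 | ½ × 0.5 = 0.25 |
| 1 | ½ × 1 = 0.5 |
| 2 | ½ × 2 = 1.0 |

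The scale is the 0–10 amount sent.

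**4. The regression as planned for Hypothesis 1b.** It adjusts for the placebo score with an estimated slope b. Holding b fixed, the bias is ½[Δ(s + c_P) − b Δ(s + c_O)]. At b = 1 this is the result in step 3. At b below 1, a group difference in s also enters, at (1 − b)/2 of its size.

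**5. The balance condition.** No balancing of sequence within diagnosis is stated. If 12 of 20 in one group and 8 of 20 in the other have placebo first, a common shift s enters the contrast of differences at (0.2 − (−0.2))s = 0.4s. Under simple randomisation (an assumption) an imbalance at least this large, in either direction, occurs about 27% of the time.

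**6. The plan's power figure.** The stated 81% reproduces as a group-by-condition interaction if the within-subject correlation is taken as 0.5, which the plan does not state: λ = 0.23² × 40 × 2/(1 − 0.5) = 8.464, power 80.9%. That corresponds to a group difference of 0.92 SD of the difference score. No SD in game dollars is given, so the biases above cannot be set against it.

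**The case against.** The strongest reply is that the mechanism is not documented. A reader might infer that participants do learn the return before Visit 3, because earnings are paid by the end of the visit. Step 2 shows why the documents do not support this: the payment sentence most naturally covers the whole study. The statement that Player 2 chooses the return belongs to the instructions given to participants; silence about a staff rule does not prove that returns are discretionary in practice. Nor does any section say that Player 2 knows the diagnosis or is presented as the same partner. All this stands, and the point must be put as an unprotected route rather than an established effect.

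A reader might also infer that the washout is the only guard against carry-over. It is not: spray order is randomised and task order is counterbalanced with carry-over in mind. But counterbalancing across participants leaves visit-to-visit learning alone, and randomised order handles only a common shift.

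Finally, a reader might infer a known downward bias in the oxytocin effect. The plan's primary tests compare diagnoses, not sprays within a group, so carry-over of equal size cancels when sequences are balanced. The sign is also open, since a poor return after a larger transfer could lower later trust. Both corrections stand. Neither protects against carry-over that differs by diagnosis.

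**Conclusion.** The concern holds as a gap in the design. The game is repeated across visits against a staff-played partner, the return is neither standardised nor withheld, and the stated protections do not cover experience that differs by drug or diagnosis. The bias is half of any BDD-control difference in c_P − c_O for the contrast of differences, and half of any such difference in the Visit 3 shift for Hypothesis 1a. The 0.25 to 1.0 range rests on an assumed group difference of 0.5 to 2 game dollars and on balanced sequences. The documents establish neither that carry-over will occur nor its direction. The change is worth making because it is cheap and protects a primary outcome. A visit or sequence term in the model would not replace it, since that removes only a common shift.

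**What to change.** 1. Generate Player 2's return by one pre-set rule, the same for all participants and both visits, with no staff choice. This closes the route through knowledge of diagnosis.
2. Disclose and pay Trust Game results only after the last game at Visit 3. This is needed as well as the rule, because a rule that depends on the amount sent would still pass a drug effect on the first transfer into the second visit.
3. Analyse the participant's transfer made before any feedback. Reconcile the task description (amount given) with Aim 1 Analyses and Power and Sample Size (back transfer); as the game is described, the latter is what the staff member returns.
4. State whether the game is played once or twice at each visit.

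I would not tell participants that each game has a new player. Steps 1 and 2 suffice, and that statement may add deception beyond the incomplete disclosure already described.

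The cost is a change to the task script and to payment timing: first-visit winnings are paid up to 28 days later. Familiarity with the task itself would remain, since withholding results removes only what is learned from the returns.
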